An independent clinical events committee (CEC), who are blinded to treatment assignment, will centrally adjudicate and validate selected endpoints where validation is necessary.

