Hospitalisation for heart failure (39, 40)	Hospital admission (lasting >24 hours) for deteriorating symptoms or signs of heart failure, where there is a documented diagnosis of heart failure and the patient receives initiation or intensification of treatment for heart failure. Initiation or intensification of treatment includes at least one of the following: increase in oral diuretic dose or addition of another oral diuretic; intravenous diuretic therapy; intravenous vasoactive therapy (vasodilator, inotrope or vasopressor); mechanical circulatory support (MCS) (including intra-aortic balloon pump (IABP), Impella, extra-corporeal membrane oxygenation (ECMO)); or cardiac transplantation.
	Heart failure during or after the assigned PCI procedure itself is defined as prolongation of the planned admission by at least 24 hours due to acute heart failure requiring initiation or intensification of treatment as defined above. Prolongation of hospital admission in patients who have prophylactic pre-PCI insertion of a mechanical support device (IABP, Impella or ECMO) should not be recorded as having a heart failure hospitalisation UNLESS there are features of heart failure requiring initiation or intensification of treatment as defined above.
	Elective admission for implantation or revision of ICD/cardiac resynchronisation therapy (CRT) devices will NOT constitute an endpoint.
Unplanned revascularisation	PCI group: Any unplanned target vessel or non-target vessel revascularisation by PCI or CABG following index PCI, excluding provisional staged PCI (with plan documented at the index procedure). OMT group: Any revascularisation by PCI or CABG.
Appropriate ICD therapy	At least one ICD shock or episode of anti-tachycardia pacing for documented ventricular tachycardia (VT) or ventricular fibrillation (VF).
Cardiovascular death	All deaths where there is no clinical or post-mortem evidence of a non-cardiovascular aetiology.

Major Bleeding

Major bleeding will be defined using the Bleeding Academic Research Consortium (BARC) categories below:

Type 3

Type 3a

- Overt bleeding plus haemoglobin drop of ≥30 to <50g/L (provided haemoglobin drop is related to bleed)
- Any transfusion with overt bleeding

Type 3b

- Overt bleeding plus haemoglobin drop ≥50g/L (provided haemoglobin drop is related to bleed)
- Cardiac tamponade
- Bleeding requiring surgical intervention for control (excluding dental/nasal/skin/haemorrhoid)
- Bleeding requiring intravenous vasoactive drugs

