8.3. Statistical Analysis

A detailed statistical analysis plan will be finalised before any analysis of the data by treatment group is undertaken. An unadjusted time-to-event analysis will be performed on the primary endpoint using data across all follow-up, with time to the first event (or censoring) times measured from randomisation. Hazard ratios together with associated confidence intervals will be calculated from the Cox proportional hazards model. The assumptions underlying the Cox model will be assessed. If there is clear non-proportionality, comparisons will also be made in early and later follow-up with cut-points determined based on availability of data prior to unblinding. Cumulative event rates will be calculated and presented using Kaplan-Meier time-to-event curves. As a measure of absolute treatment difference, cumulative event rates will be compared at 2 years. Secondary analyses of each individual component of the primary composite endpoint as well as other secondary time to event outcomes will be analysed using the above methods. Losses to follow-up are expected to be minimal and patients will be included up until the time they experience the event or are censored.

Any categorical outcome measures will be examined at specific time points using risk ratios or risk differences, confidence intervals and chi-square or Fisher's exact tests as appropriate. Continuous variables will be analysed and presented as mean treatment differences, confidence intervals and p values derived from analysis of co-variance models or unpaired t-tests as appropriate (with appropriate transformation if necessary). Analysis of endpoints in the randomised cohort will be by intention-to-treat.

A limited number of subgroups for the primary endpoint will be pre-specified in the analysis plan and are likely to include groups stratified by age, the extent of coronary disease (BCIS-1 JS <12 vs. 12), degree of LV dysfunction (EF <20% vs. ≥20%), diabetes, NYHA class (<3 vs. ≥3) and chronic total occlusion (CTO). In addition, a model will be developed and patients will be categorised according to their baseline risk of the primary outcome and this will be used to examine whether the impact of treatment depends on a person's underlying risk. Since the subgroup analyses are secondary analyses and exploratory in nature, the trial has not been

powered for these. A Cox proportion hazards model incorporating tests of interaction will be used for subgroup analyses.

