Imaging and intervention specialists at each participating centre will adjudicate segmental viability and the feasibility of revascularising the relevant segments, to determine whether an individual patient will be eligible for randomisation.

12. Randomisation

Potential patients will be reviewed by the Principal Investigator before randomisation with all available tests/notes to confirm eligibility.

Once the eligibility of a patient is confirmed by the trial coordinators and written informed consent obtained, randomisation will be carried out via an online web based system. Randomisation of the treatment assignment will be stratified by centre using randomly permuted blocks of varying size, with 1:1 allocation between the PCI and OMT arms.

There is no time limit from randomisation to PCI. However, it is recommended that index PCI be carried out as close as possible to randomisation to minimise the incidence of major adverse cardiovascular events (MACE) prior to the assigned treatment. Clinical events that occur after randomisation but before planned PCI will be attributed to the assigned treatment on an intention-to-treat basis.

13. Percutaneous Coronary Intervention

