9.3 Analysis of Other Secondary Endpoints

Analysis of secondary outcomes will be based on the ITT population unless otherwise stated below.

- (1) Cardiovascular death over the entire duration of follow-up
- (2) All-cause death over the entire duration of follow-up
- (3) Hospitalisation due to heart failure over the entire duration of follow-up

- (4) Acute MI over the entire duration of follow-up (until last scheduled annual follow-up visit)
- (5) Appropriate ICD therapy to 2 years post randomisation
- (6) Unplanned further revascularisation over the entire duration of follow-up (until last scheduled annual follow-up visit)
- (7) CCS class at 6 months, 1 year and 2 years post randomisation
- (8) NHS Resource use
- (9) Brain natriuretic peptide (BNP or NT-Pro BNP) level at 6 months, 1 year and 2 years post randomisation
- (10) Major bleeding to 2 years post randomisation (recorded post PCI, 6 months,1 year and 2 years)

The above secondary time to event outcomes (1-6) will be analysed using the same methods as described for the primary outcome (Section 9.1). CSS class, which is an ordinal outcome measure scored 0-4, will be analysed using the same methods as described for 'NYHA Functional Class' outcome (Section 9.2.3). Analysis of NHS resource use is described in the health economics outcome section (Section 11). Differences in mean BNP or NT-Pro BNP between treatment groups at each timepoint will be calculated using a linear mixed model with treatment group, categorical treatment by timepoint interaction and baseline BNP or NT-Pro BNP in the model (random intercept, unstructured correlation) as described for % LVEF (Section 9.2.1). It may be necessary to examine BNP or NT-Pro BNP for transformations to adhere to the assumptions of the linear mixed model or use bootstrapping techniques if a suitable transformation cannot be found.

Major bleeding will be summarised as the cumulative frequency and percentage at each time point by treatment group. The treatment groups will be compared at 1 and 2 years using a risk ratio, 95% confidence interval and likelihood ratio test p-value from a binomial regression model.

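### Unplanned revascularisation is counted only after the index PCI in the PCI arm but without restriction in the OMT arm, which tilts this secondary endpoint towards PCI

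*Protocol*

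**What the plan says.** Protocol section 4.4 gives two definitions of unplanned revascularisation:

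- PCI arm: "PCI group: Any unplanned target vessel or non-target vessel revascularisation by PCI or CABG following index PCI, excluding provisional staged PCI", where the plan for staging was recorded at the index procedure.
- OMT arm: "OMT group: Any revascularisation by PCI or CABG".

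Protocol section 8.3 sets the clock for the primary endpoint as "time to the first event (or censoring) times measured from randomisation" and adds that "other secondary time to event outcomes will be analysed using the above methods". SAP section 9.3 applies the primary-outcome methods of SAP section 9.1 to unplanned revascularisation, item 6 of its list: time from randomisation, intention to treat, Cox model.

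Protocol section 12 states: "There is no time limit from randomisation to PCI". It then recommends that the index PCI follow randomisation closely, and adds: "Clinical events that occur after randomisation but before planned PCI will be attributed to the assigned treatment on an intention-to-treat basis".

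Protocol section 13.3 counts an urgent revascularisation done ahead of a planned second stage as a major endpoint. SAP section 5.2 expects some PCI-arm patients not to receive the PCI as intended and says they will be described. Protocol section 4.3 lists this endpoint among the other secondary endpoints.

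**The concern.** Both arms share a time origin but not a start of counting. In the PCI arm, the time between randomisation and the index PCI is time at risk in which no event can be recorded. For a patient who never has an index PCI, that is the whole of follow-up. The OMT arm has no such interval.

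Take two patients who each need CABG six weeks after randomisation. The OMT patient has an event. The PCI-arm patient still waiting for PCI does not, because nothing has yet happened for the CABG to follow.

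At stake are the hazard ratio and the 2-year difference for an endpoint that readers will use to judge how often each strategy ends in an unintended procedure. With equal true rates in the two arms, the definition alone would make PCI look better.

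**Working it through.** **Comparing the passages**

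| Situation after randomisation | OMT arm | PCI arm, as written |
|---|---|---|
| CABG, no index PCI yet | event | not an event |
| Urgent PCI for ACS, no planned index PCI yet | event | not an event; may itself be taken as the index PCI |
| CABG in a patient who never has an index PCI | event | not an event |
| Urgent procedure after stage 1, before planned stage 2 | not applicable | event (section 13.3) |
| Unplanned procedure after the index PCI | not applicable | event |
| Assigned index PCI and its documented stages | not applicable | not an event, correctly |

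The first three rows are the difference between the arms. Section 13.3 does not help, since it starts after the first stage. SAP sections 3.4 and 9.3 repeat the endpoint without changing its definition.

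**Figures in the plan**

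The documents give no event rate, power or expected wait for this endpoint. The only event-based figure is the primary-endpoint power: 300 events, hazard ratio 0.7, 5% significance (taken as two-sided). By Schoenfeld's formula, √300 × |ln 0.7| / 2 − 1.96 = 3.089 − 1.960 = 1.129, which gives 87.1% and agrees with the stated figure of over 85%. Unplanned revascularisation is not part of the primary composite, so this power does not change.

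**Illustration of size**

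Assumptions, none of them from the documents:

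- The true rate is constant and equal in both arms (no treatment effect), at 5% per year.
- Every PCI-arm patient waits the same time d (in years).
- No PCI-arm procedure during d counts.

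With 350 patients per arm (from the plan) and follow-up T = 2 years:

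- OMT risk = 1 − 0.95^T = 1 − 0.95² = 0.0975
- PCI-arm recorded risk = 1 − 0.95^(T − d)
- Patients lost = 350 × (OMT risk − PCI-arm risk)

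| Wait d | PCI-arm recorded risk | Risk ratio | Patients lost of 350 |
|---|---|---|---|
| 1 month | 0.094 | 0.96 | 1.4 |
| 3 months | 0.086 | 0.88 | 4.1 |
| 6 months | 0.074 | 0.76 | 8.2 |

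**Sensitivity to the assumptions**

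- Rates of 3% to 10% per year: 2-year ratios of about 0.96, 0.88–0.89 and 0.76–0.77 for the three waits.
- Four years of follow-up, same rates: about 0.98, 0.94–0.95 and 0.88–0.90.
- Hazard three times higher in the first 6 months, over 2 years: about 0.92–0.93, 0.76–0.78 and 0.51–0.54.
- If a fraction f of PCI-arm patients never has an index PCI, the PCI-arm recorded risk is about (1 − f) times that of an arm in which all do. The documents do not give f.

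The direction is towards PCI in every case. The third assumption makes these figures high for a given wait and rate if an urgent PCI during the wait is properly regarded as the assigned treatment delivered early.

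**The case against.** The strongest reply is that much of the asymmetry belongs to the design. The trial compares strategies. The first PCI in the PCI arm is the assigned treatment, whereas in the OMT arm any revascularisation departs from the initial strategy. On that view, a PCI brought forward because of an ACS delivers the assigned strategy and is not a failure of it. This stands in part: the assigned PCI cannot be an event in its own arm, and how to class an expedited PCI is a judgement. It does not cover CABG or another non-assigned procedure before the index PCI, or patients who never have one. Excluding those is avoidable.

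The consequences are also limited. Section 12 recommends prompt PCI, so long waits are not what the plan intends. An ACS during the wait that meets the MI definition is still captured as MI. The SAP also undertakes to report PCI timing and the patients who did not receive PCI as planned. All of this stands, and it bears on size and visibility; it does not correct the comparison.

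A reader might infer two stronger points that the documents do not support:

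- *That section 12 contradicts section 4.4.* Section 12 says to which arm an event before PCI belongs. It does not say what qualifies as an event, so both passages can be followed at once.
- *That a blinded committee could not apply the definition.* The committee, "blinded to treatment assignment, will centrally adjudicate and validate selected endpoints", is not said to adjudicate this one. Even if it did, it could validate dates and reasons and leave the arm-specific rule to the analysis.

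**Conclusion.** The difference between the arms and its direction follow from the wording of section 4.4 read with the time origin in section 8.3 and SAP section 9.3. No other passage removes it. Unplanned or non-assigned procedures before, or instead of, the index PCI are uncountable in the PCI arm only, and the endpoint is biased towards PCI.

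The size rests on a wait and a rate that the documents do not give. With prompt PCI it is small: about 1.4 of 350 patients and a 2-year ratio of about 0.96 at 5% per year and a 1-month wait, or about 4.1 patients and 0.88 at 3 months. The 6-month case (about 0.76) and the front-loaded hazards show only how the bias grows. They should not be read as estimates for this trial, given its recommendation to do PCI early.

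The primary endpoint and its power are unaffected. The definition should be corrected, but this does not threaten the trial's main conclusion.

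**What to change.** Replace the two arm-specific sentences in protocol section 4.4 with one rule, and apply it to item 6 in SAP section 9.3. The event, counted from randomisation in both arms, is any revascularisation by PCI or CABG other than the assigned index PCI and its documented stages. Any CABG or unplanned non-assigned procedure before or instead of the index PCI then counts on its own date.

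State one rule, fixed before unblinding, for whether an urgent PCI for ACS during the wait is an event or delivery of the assigned PCI. Run a sensitivity analysis with the other classification. The rule still treats the assigned PCI differently by arm, as it must.

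The cost is one sentence in the protocol and its counterpart in the SAP, some reclassification, and a few more PCI-arm events. SAP section 7.6 already lists the staging and timing of PCI, and SAP section 9.3 the reason for and type of revascularisation. The case report form is not shown, so confirm that it records why a PCI-arm patient's first procedure was done.

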8.2. Crossover

In patients randomly assigned to receive OMT, revascularisation by PCI or CABG during the trial should only be considered in one of the following circumstances:

- Readmission with an acute coronary syndrome (ACS), including ST-elevation myocardial infarction (STEMI) and non-STE events. The diagnosis of ACS will be based on the presence of typical ischaemic symptoms as well as a rise in cardiac biomarker levels or dynamic ST deviation on ECG.
- Deterioration in exertional angina to ≥CCS class 3 level symptoms.
- Resistant ventricular arrhythmias considered to be ischaemic in aetiology.

This trial will be a comparison of strategy, rather than technique, and the projected event rates and hazard ratio allow that OMT patients may undergo subsequent revascularisation. As such, no additional adjustments have been made to the power calculation to account for unplanned revascularisation in the OMT arm.

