13.2. Completeness of Revascularisation

It is strongly recommended that PCI is considered and, if feasible, attempted on all significant coronary lesions in major proximal coronary vessels (or side branches >2.5mm in diameter) subtending viable myocardium. Lesion significance is defined as >70% diameter stenosis on angiography or for lesions between 50 and 70% diameter stenosis, when accompanied by

demonstrable reversible ischaemia on invasive or non-invasive testing. Planned target lesions will need to be identified by the operator and recorded by the trial coordinator before the procedure.

Patients who meet inclusion criteria and have CTO of coronary arteries subtending viable myocardial segments *should* be considered for REVIVED, provided that the PCI operators predict a high likelihood of successfully reopening these vessels. It is recommended that dedicated CTO operators, in units that have this degree of specialisation, undertake such cases.

The coronary disease burden at baseline and the degree of final revascularisation will be characterised by the BCIS-1 JS and Revascularisation Index (RI) (44), where $RI = (JS_{pre} - JS_{post})/JS_{pre}$.

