13.3. Staged PCI

A single stage strategy should be employed where possible. However, provisional staging could be considered in patients with renal dysfunction, complex coronary disease (including chronic total occlusions) or if it is felt during PCI that deferring intervention to one or more vessels is in the patient's best interests (e.g. due to unexpected high contrast volumes or procedural complications during PCI to the first vessel). Staging must be pre-specified at the index procedure.

Urgent revascularisation before the planned 2nd stage procedure will be considered a major endpoint(45).

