Appropriate ICD therapy will be assessed, on an ITT basis, in the cohort that had undergone device implantation before randomisation or within 90 days of randomisation. The main analysis will only include centre-reported ICD data up to 2 years from randomisation. Longer term ICD-derived outcomes will be the subject of a separate sub-study. See also section 9.6.2 below.

For death, MI, unplanned revascularisation, heart failure hospitalisation and appropriate ICD therapy outcomes, further details of these outcomes will be REVIVED SAP

summarised by treatment group (e.g. primary causes of death, NSTEMI or STEMI, reason for revascularisation and type of revascularisation, days in hospital, types of therapies). Continuous variables will be described by the means and standard deviation. Alternatively for skewed variables they may be described by the median and IQR. Categorical variables will be described by frequency and percentages in each category.

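### Unplanned revascularisation: a non-urgent, symptom-driven PCI on a vessel deferred in a documented index plan can go uncounted in the PCI arm, while the same procedure counts in the OMT arm

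*Protocol*

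**What the plan says.** Protocol section 4.4 defines the endpoint separately by arm. In the PCI group any unplanned PCI or CABG after the index PCI counts, on target or non-target vessels, "excluding provisional staged PCI (with plan documented at the index procedure"). For the other arm it reads "OMT group: Any revascularisation by PCI or CABG".

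Section 13.3 prefers a single stage where possible. It allows provisional staging on three grounds: renal dysfunction, complex anatomy (chronic total occlusions among them), and a clause that reads "if it is felt during PCI that deferring intervention to one or more vessels is in the patient's best interests". It adds two limits: "Staging must be pre-specified at the index procedure", and "Urgent revascularisation before the planned 2nd stage procedure will be considered a major endpoint".

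Section 13.2 says "Planned target lesions will need to be identified by the operator and recorded by the trial coordinator before the procedure". Section 8.2 lists three circumstances in which OMT patients should be considered for revascularisation, one of them "Deterioration in exertional angina to ≥CCS class 3 level symptoms".

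Unplanned further revascularisation is listed in 4.3 among the other secondary endpoints. SAP section 9.3 analyses it over all follow-up to the last scheduled annual visit, with the methods used for the primary outcome, and says that "reason for revascularisation and type of revascularisation" will be summarised by arm. SAP section 7.6 records staging and timing of PCI.

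**The concern.** The exclusion in 4.4 depends on one fact: that a provisional plan was written at the index procedure. It does not ask whether the later PCI treated the lesion or vessel that was deferred, how long after the index procedure it took place, or why the patient came back. Section 13.3 tests the reason only as far as urgency.

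That leaves one kind of procedure without a rule. A PCI patient with a stage on record develops worse angina and later has the deferred vessel treated electively. Under 4.4 this need not be an event. An OMT patient with the same deterioration meets a listed 8.2 circumstance, and the resulting PCI is an event.

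The trial is open-label and the plan is written by the treating team. The endpoint gets its own hazard ratio, confidence interval and p-value, and SAP section 6.5.4 makes no multiplicity adjustment. What is at stake is whether a reported difference in unplanned revascularisation reflects patients' need for procedures or the counting rule.

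**Working it through.** **1. The rules side by side.**

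| Later procedure | PCI arm | OMT arm |
|---|---|---|
| No stage documented at index | Counts (4.4) | Counts (4.4) |
| Stage documented, urgent procedure before stage 2 | Counts under 13.3; 4.4 is silent | Not applicable |
| Stage documented, elective, done because of the plan | Excluded (4.4) | Not applicable |
| Deferred vessel, elective, prompted by new or worse symptoms | Excluded on the wording of 4.4; not caught by 13.3 | The same symptoms leading to PCI count |

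The last row is the gap. No section of the protocol or SAP sets a maximum interval between stages, defines urgent, or ties the 4.4 exclusion to the lesions recorded under 13.2.

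**2. The label.** Section 4 has primary, major secondary and other secondary endpoints, so the major endpoint of 13.3 matches none of them for revascularisation. The label has a consequence. Section 4 of the protocol limits blinded adjudication to selected endpoints, and SAP section 4.3 extends it to all major endpoints. Whether these events are adjudicated therefore depends on a category that the documents do not settle.

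**3. The plan's own figure.** No event rate or power is stated for this endpoint. The stated power for the primary endpoint (300 events, hazard ratio 0.7, two-sided 5%) reproduces by Schoenfeld's formula: Φ(√300/2 × |ln 0.7| − 1.96) = Φ(3.089 − 1.960) = 87.1%, against the stated figure of over 85%. It is not touched, because revascularisation is outside the composite.

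**4. Illustration on assumed values.** Inputs: 350 patients per arm (section 8.1); the same true risk *p* in both arms (assumed 5%, 10%, 15%); a share *m* of PCI-arm events labelled staged (assumed 10%, 20%, 30%). The counted PCI-arm risk is *p*₂ = *p*(1 − *m*).

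- Apparent hazard ratio = ln(1 − *p*₂)/ln(1 − *p*).
- Chance of a significant result favouring PCI = Φ([(*p* − *p*₂) − 1.96·SE₀]/SE₁), where SE₀ and SE₁ are the pooled and unpooled standard errors of the difference in proportions.

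Example with *p* = 0.10 and *m* = 0.20: *p*₂ = 0.08. The hazard ratio is ln 0.92/ln 0.90 = 0.791. The chance is Φ([0.02 − 1.96 × 0.02163]/0.02162) = Φ(−1.036) = 15.0%.

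| True risk, both arms | *m* = 10% | *m* = 20% | *m* = 30% |
|---|---|---|---|
| 5% | HR 0.898; 5.0% | HR 0.796; 9.3% | HR 0.695; 16.4% |
| 10% | HR 0.895; 6.6% | HR 0.791; 15.0% | HR 0.689; 29.5% |
| 15% | HR 0.892; 8.2% | HR 0.787; 21.2% | HR 0.683; 43.0% |

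With no true difference the nominal chance in that direction is 2.5%. The apparent hazard ratio depends almost entirely on *m*, which the documents do not allow anyone to estimate.

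**The case against.** A reader might infer that any repeat PCI months later can simply be called staged. The documents do not support that. The plan must exist at the index procedure (4.4 and 13.3), and without it the procedure counts. Nor is the reason wholly untested, since 13.3 counts urgent revascularisation before the second stage. Staging is discouraged where a single stage is possible, and SAP section 8.1 speaks of index PCI close to randomisation as one or two stages, so a long-open plan should be uncommon. These points stand, and they confine the concern to patients with a documented plan and a non-urgent return.

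Part of the asymmetry is inherent. The OMT arm has no planned PCI to exclude, and 8.2 calls the trial a comparison of strategy. That justifies leaving out procedures done because of the plan. It does not justify leaving out those done because symptoms worsened.

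A reader might also conclude that the whole comparison favours PCI. That goes too far. Section 8.2 restricts revascularisation in OMT patients and no matching restriction is stated for repeat procedures in the PCI arm, which may pull the other way. The exclusion itself, however, works in one direction only.

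The events committee could settle the classification. But the rule is already fixed in the 4.4 definition, and the documents do not say that this endpoint is adjudicated.

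**Conclusion.** The point holds in a limited form. For PCI patients with a stage documented at index, the counting rule can drop an elective, symptom-driven PCI on the deferred vessel, at any interval, when the same deterioration leading to PCI in an OMT patient counts. Sections 4.4 and 13.3 also disagree on urgent procedures, and the label in 13.3 does not fit 4.3.

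The mechanism can only remove PCI-arm events. How many is unknown. The hazard ratios of about 0.9, 0.8 and 0.7 rest on assumed risks and assumed shares and show sensitivity, not an expected bias. The effect is confined to one other secondary endpoint. It is worth correcting because the correction is cheap.

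**What to change.** These changes concern counting only; they do not bear on when or whether a stage is performed.

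- In 4.4, exclude a later PCI as staged only if it treats a lesion or vessel deferred in the documented index plan, is elective, and has the plan as its recorded reason. It should count if the reason is a new acute coronary syndrome, a deterioration in angina from baseline to CCS class 3 or worse, or a ventricular arrhythmia as worded in 8.2. The comparison with baseline is needed because 6.2 does not exclude patients who already have such angina at entry.
- Add a sensitivity analysis that counts revascularisation for an 8.2 indication in both arms.
- Report the time from index PCI to each excluded stage. This is preferable to a fixed cut-off such as 90 days, which has no basis in the documents and would turn planned late stages into events.
- Define urgent for endpoint purposes, carry the 13.3 rule into 4.4, and reconcile the major endpoint label with 4.3.

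The cost is protocol and SAP wording plus some review. Staging, timing, and the reason for and type of revascularisation are already in the SAP (7.6 and 9.3). It is not stated whether a reason is also captured for procedures entered as stages, so the recorded reason must be reviewed for each one. A few genuinely planned stages may be counted as events.
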